# **Supportive Care Guidelines:**

In general, concomitant medications and therapies deemed necessary for the supportive care and safety of the subject are allowed, provided their use is documented in the medical records.

# **b. Study Duration**

The time commitment to study participants is approximately 1.25 months. This includes the 1-day pretest baseline, 7 days of twice daily interventions during wound care procedures, and follow-up at 1 day, 1 week and 1 month after the 14th wound care procedure on study day 7. Duration of individual subject treatment will depend on individual response and tolerance.

# c. Blinding

The Safety, Efficacy and Opiate-Sparing Effects of Ketamine for Acute Burn Wound Care Pain in a Setting Analogous to Austere Battlefield Conditions (IRB00089761) provides for 3-levels of blind: nurse at bedside, patient-participant, and research assistant with the following methods:

The investigational pharmacy will provide blinded medications (i.e., usual care with normal saline or usual care with ketamine augmentation) for this study (for details, see above). The provider will order the medications, the pharmacy will fill the order in identical delivery systems and deliver it to Pyxis in the BICU, thus resulting in blinding to the content of the injections and infusions for the nurse who administers these medications, the research assistant and the patient. This is necessary to ensure fidelity of procedures and validity of findings, responses, observations and data collection. This procedure reduces the possibility that preconceived notions could influence clinical or research personnel or participant in the study.

# d. Justification of why participants will not receive routine care or will have current therapy stopped. $N\!/\!A$

**e. Justification for inclusion of a placebo or non-treatment group.** (see above background and design for purpose of saline placebo and blinding, respectively). There is no "non-treatment group" - both groups receive usual care - fentanyl. Blinding by pharmacy preparation of the drug and delivery system in identical, nondescript pump formats for both groups is standard in drug trials in order to prevent bias to confound prescription, observations, data recording, etc. There are actually 3-levels of blind in this project: Nurse at bedside, Patient/participant, and, research assistant.

**f. Definition of treatment failure or participant removal criteria.** Should a patient decide to withdraw, all efforts will be made to complete and report the observations as thoroughly as possible. Reasons for premature withdrawal may include:

- Disease progression
- Unacceptable adverse events.
- Intercurrent illness that prevents further administration of treatment or would affect assessment of clinical status to a significant degree.
- Initiation of non-protocol therapy for the disease under study.
- Non-compliance with protocol or treatment.
- Subject becomes pregnant.
- g. What happens to participants receiving therapy when study ends or if a participant's participation in the study ends prematurely

When the study ends or when a participant's participation ends prematurely, he/she will continue to receive usual care treatment.

# 5. Inclusion/Exclusion Criteria (see above) See Item #4 Study Procedures

# 6. Drugs/ Substances/ Devices

a. The rationale for choosing the drug and dose or for choosing the device to be used. (see discussion in item #3 Background. Ketamine is being administered in accordance with the FDA guidelines for this medication as an analgesic medication for acute pain.

# 7. Study Statistics

- a. Primary outcome variable. Described above (Outcomes)
- b. Secondary outcome variables. Described above (Outcomes)
- c. Statistical plan including sample size justification and interim data analysis. Described above

Statistical consultation and initial power estimation were obtained from the Johns Hopkins Biostatistics, Epidemiology, and Database program (BEAD). The Johns Hopkins Institute for Clinical and Translational Research (ICTR) worked with the Ketamine Team to develop the randomization model and the REDCap Database and will continue to serve as consultants throughout the duration of the study. The ICTR expertise will be of particular importance when managing issues such as data cleaning and preparation, preparing interim reports, and in designing and conducting both preliminary and final statistical analyses. Using standard methods, the BEAD suggested that a total sample size of 74-94 participants (n= 37-47 per Condition) should be sufficient to provide a power of .85 to detect a statistically significant difference at p < 0.05. This study team has discussed this issue of power and decided to be conservative and enhance the opportunity of making a definitive statement regarding study objectives and secondary questions. Therefore, the total target sample size will be increased to n= 100. One clarification is important: Funding is for a 1-year period. Should funding end before 94 participants are enrolled the study will have more than sufficient power to address the primary objectives (n=74).

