3. Sample Size and Power Estimations – Additional Biostatistics, Epidemiology And Database Resources [name], Psychologist, Statistician

[name], Epidemiologist/Biostatistician, Statistician

Drs. [name] and [name] participated in planning, executing, interpreting and writing/illustrating the rich analyses of primary (i.e., pain severity, opiate sparing), and secondary (i.e., symptoms of PTSD and depression) aims. The Biostatistics, Epidemiology and Data Management Core (BEAD) is a recognized research Core of the JHU School of Medicine which provides research support services to faculty and trainees. With sponsored funds from the Vice Dean for Research of the Bayview Medical Campus, BEAD Core research support will be available to support this research project. At a minimum, this can include 60 hours of support services to include research support, trainee career development and subsequent grants development activities based on the results of this investigation.

Furthermore, the sponsored research resources of ICTR will stretch the budget and allow the Ketamine Project to optimize the rigor in database design and management, as well as with overall biostatistical guidance leveraging the Core's team of Masters and PhD level biostatisticians and epidemiologists with wide ranging content and methodologic expertise. Engagement of these services will ensure the quality of the data being compiled, integrated and utilized as this is a vital component of the success of the intervention project and the overall objectives of the study through the engagement in the development of the database structure, variable coding, data input, data manipulation and transformations required for the seamless transition for the conduct of analyses.

The sample size estimates described next were generated by [name], BEAD statistician, as Co-Investigator on the project for the role and tasks delineated here. The next two paragraphs describe the methods and conclusions used by [name] to Estimate sample sizes for:

- 1. Sample Size Estimate: 7-day LOS, as originally planned, and
- 2. Sample Size Estimate/Corrected: 7-Day LOS as corrected to 5.5 Days (11 wound care sessions see rationale below) due to uncertainties not always evident or predictable on the first day of admission but which may affect/reduce LOS for any given patient.

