#### 1. Sample Size Estimate Based on Stay $\geq$ 7 days in Burn ICU.

The sample size calculation is based on the primary statistical procedure for this project which will test the difference in mean pain scores, defined as the average self-report of mean pain score, based on the Numeric Analogue Scale (NAS), during each burn wound care procedures, between individuals randomized to usual care plus placebo (fentanyl plus saline) and those randomized to the intervention arm (usual care + ketamine). PASS Sample Size (Version 14) was used to perform all sample size calculations while considering individuals over the one-year study duration randomized to control and intervention arms in a 1:1 fashion.

In the first case, we further assume that each individual, will, on average, have a length of stay of 7 days thus resulting in 14 wound care procedures performed during hospital stay. We determined the minimum sample size for our trial based on 80% power at p = 0.05 to detect a clinically significant difference in mean pain score during the wound care procedure of 2.0 points between the control and intervention arms with a standard deviation of 3.0. In addition, to account for the clustered nature of procedures performed on individuals, we have used a sample size inflator (also termed "design effect") of 10.1 as described by the Cochrane manual@ conservatively using an interclass correlation of effects of 0.7 amongst repeated measures of pain scores within each individual and 14 observations per individual.

The required sample size needed to accept the alternative hypotheses that the mean pain care score in the intervention arm decreased by 2 points compared to the control arm at the 0.05 level would require 27 individuals per arm (54 total), our anticipated population of 74 eligible individuals is adequate to show a clinically significant improvement for both intervention arms.

@http://handbook.cochrane.org/chapter\_16/16\_3\_4\_approximate\_analyses\_of\_cluster\_randomized\_trials\_for\_a.htm

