#### 2. Corrected Sample Size Estimate for Length of Stay on the Burn ICU $\geq$ 7 days as **estimated on Admission** but, however, where the **Actual Length of Stay on Burn ICU is** $\geq$ **5.5 days** because of Factors that either not present or not evident or were difficult to quantify at time of admission and consent of the patient.

This sample size calculation is based on the primary statistical procedure for this project which will test the difference in mean pain scores, defined as the average self-report of mean pain score, based on the NAS, during each burn wound care procedures, between individuals randomized to usual care (fentanyl plus saline) and those randomized to the intervention arm (usual care + ketamine). PASS Sample Size (Version 14) was used to perform all sample size calculations eligible individuals over the one-year study duration randomized to control and intervention arms in a 1:1 fashion.

In this situation, where Length of Stay is less than the initially estimated >7 days, we further assume that each individual, will, on average, have a length of stay of 5.5 days on the Burn ICU thus resulting in 11 wound care procedures

performed during hospital stay on the Burn ICU. We determined the minimum sample size for our trial based on 80% power at p = 0.05 to detect a clinically significant difference in mean pain score during the wound care procedure of 2.0 between the control and intervention arms with a standard deviation of 4.0. In addition, to account for the clustered nature of procedures performed on individuals, we have used a sample size inflator (also termed "design effect") of 8.0 as described by the Cochrane manual@ conservatively using an interclass correlation of effects of 0.7 amongst repeated measures of pain scores within each individual and 11 observations per individual.

The required sample size needed to accept the alternative hypotheses that the mean pain care score in the intervention arm decreased by 2 points compared to the control arm at the 0.05 level would require 47 eligible individuals (94 total), our anticipated population of 128 eligible individuals is adequate to show a clinically significant improvement for both intervention arms.

@http://handbook.cochrane.org/chapter\_16/16\_3\_4 approximate analyses\_of\_cluster\_randomized\_trials\_for\_a.htm

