#### **Changes Requested:**

- a. Inclusion and length of stay clarifications:
  - The length of stay for our protocol had been set at ≥7 days estimated at time of admission to the burn center. However, the number of days a patient remains in the BURN ICU is highly variable, and dictated by factors difficult to accurately quantify when first admitted. For example, patients leave against medical advice, to seek drugs or alcohol, to return to work, or attend to financial matters. For example, some patients may leave the BURN ICU earlier than was originally estimated due to faster wound healing. Others may proceed to the OR for surgical closure of the wounds prior to 7 days, which typically changes the type and duration of wound care for several days after surgery. The length of ICU stay of others may decrease due to an initial overestimate of wound severity and, hence, a reduced need for close ICU monitoring and a reduced likelihood that the patient would remain in the BICU for 7 or more days.
  - b. Inclusion requirement clarification 1: While retaining the inclusion criteria as estimated LOS  $\geq$ 7 days at time of admission, we request a Change in Research such that the actual minimum number of days spent on the BICU be changed to achieve an average LOS of  $\geq$ 5.5 days. The actual number of wound care sessions is to range from 3-7 days and the range in sessions to be from 3 (1/day for 3 day length of stay) to 14 (2/day days at 2 sessions/day plus 1 session on last day), respectively.

These two ranges (i.e., average LOS  $\geq$ 7 days, average LOS  $\geq$ 5.5 days) were used in estimating two sets of power estimates, sample size and in participant accrual. However, data will be considered on an intent to treat basis for those participants with less than 7 treatment days and less than 14 wound care sessions due to abbreviated stay on ICU, surgery for wound closure that obviates further wound care, or who are discharged early.

C. Inclusion requirement clarification 2: Similarly, there are some patients who are ordered to receive only one dressing change per day rather than the usual two per day, while, rarely, some may be scheduled for 3 wound care sessions on certain days. Data on any participants who are otherwise eligible for the Ketamine Trial but who are ordered to have daily wound care procedures  $\geq 2/day$  or  $\leq 2/day$  will be considered on an intent to treat basis.

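### Section 7 claims power .85 at 74 to 94 participants, but the protocol's two sample-size calculations give about .91 to .96 or .70 to .80, and they differ only through an unexplained change of SD from 3.0 to 4.0

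*Combined protocol and SAP*

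**What the plan says.** Section 7 (Study Statistics, item c) states that "a total sample size of 74-94 participants (n= 37-47 per Condition) should be sufficient to provide a power of .85" at the 0.05 level. It then raises the target to 100 and adds: "Should funding end before 94 participants are enrolled the study will have more than sufficient power to address the primary objectives (n=74").

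The calculations are in Section 4, under Sample Size and Power Estimations.

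- **Item 1** assumes a stay of 7 days and 14 wound care sessions. It takes 80% power to detect a difference of "2.0 points between the control and intervention arms with a standard deviation of 3.0", with an intraclass correlation of 0.7 and a design effect of 10.1. It requires 27 per arm, 54 in total, and concludes that "our anticipated population of 74 eligible individuals is adequate".
- **Item 2** is headed as a corrected estimate, described in the introduction as "7-Day LOS as corrected to 5.5 Days". It assumes 11 sessions and 80% power to detect a difference of "2.0 between the control and intervention arms with a standard deviation of 4.0", with the same correlation and a design effect of 8.0. It "would require 47 eligible individuals (94 total").

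Under Changes Requested, item b, the protocol says the two length-of-stay assumptions "were used in estimating two sets of power estimates, sample size and in participant accrual". The Data Analysis Plan attributes the power estimate to one cited study but quotes no SD, correlation or effect from it.

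**The concern.** The top of Section 7's range, 94, is the output of item 2, where it carries 80% power, not .85. The bottom, 74, is not the output of any power calculation. It is the annual average number of admissions staying at least 7 days (Table 1), which item 1 uses as the available population.

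The second problem is the reason given for the corrected estimate. The text speaks only of shorter and less predictable stays, while the SD moves from 3.0 to 4.0 without comment.

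This matters because funding is for one year and the protocol declares in advance that 74 is enough. If the trial ended there with a null result, Section 7 could be cited to present it as well-powered evidence of no benefit. On the protocol's own corrected inputs, that reading would be wrong.

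**Working it through.** **Inputs** (Section 4, Sample Size and Power Estimations, items 1 and 2): difference 2.0; SD 3.0 or 4.0; intraclass correlation 0.7; m = 14 or 11 sessions; alpha 0.05; power 80%; 1:1 allocation. Sidedness is not stated. Two-sided is assumed because it reproduces both stated sample sizes and one-sided testing does not.

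**Formulas.** Design effect DE = 1 + (m − 1) × 0.7, which is 10.1 for m = 14 and 8.0 for m = 11. Patients per arm = n × DE/m, where n is the per-arm number for independent observations. The SD of a patient's mean over m sessions is SD × √(DE/m). Power is that of a two-sample t-test on patient means.

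**Step 1: reproduce the protocol's figures.** For 80% power, n is 37 at SD 3.0 (36.3 rounded up) and 64 at SD 4.0 (63.8 rounded up).

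- Item 1: 37 × 10.1/14 = 26.7, so 27 per arm and 54 in total, as stated.
- Item 2: 64 × 8.0/11 = 46.5, so 47 per arm and 94 in total, as stated.

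**Step 2: separate the effect of stay from that of SD.**

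| SD | Sessions | Calculation | Per arm |
|---|---|---|---|
| 3.0 | 14 | 37 × 10.1/14 = 26.7 | 27 |
| 3.0 | 11 | 37 × 8.0/11 = 26.9 | 27 |
| 4.0 | 14 | 64 × 10.1/14 = 46.2 | 47 |
| 4.0 | 11 | 64 × 8.0/11 = 46.5 | 47 |

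With a correlation of 0.7, DE/m moves only from 0.721 to 0.727 when sessions fall from 14 to 11. The stay has no effect on the rounded requirement. The SD accounts for all of the rise from 54 to 94.

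**Step 3: power at the numbers Section 7 uses.**

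| Inputs | SD of patient mean | N = 74 | N = 94 | N = 100 |
|---|---|---|---|---|
| SD 3.0, 14 sessions (item 1) | 2.548 | 91% | 96% | 97% |
| SD 3.0, 11 sessions | 2.558 | 91% | 96% | 97% |
| SD 4.0, 14 sessions | 3.397 | 70% | 81% | 83% |
| SD 4.0, 11 sessions (item 2) | 3.411 | 70% | 80% | 83% |

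On item 2's inputs, power is 84% at 104, .849 at 106 and .855 at 108, so .85 needs 54 per arm.

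**Step 4: look for inputs that would give .85.**

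- With 11 sessions, .85 requires an SD of 3.32 at N = 74 or 3.75 at N = 94. Neither value is in the documents.
- One-sided testing at SD 4.0 with 11 sessions gives .81 at 74 and .88 at 94.
- Dropping the design effect at SD 3.0 gives .81 to .82 at 74 and .89 to .90 at 94.

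**The case against.** The strongest reply is that the .85 is a floor. The sentence says the range should be enough to provide .85, and on item 1's inputs both ends exceed it. That stands for item 1: on SD 3.0, calling 74 more than sufficient is true. It does not help with item 2, the calculation the protocol presents as the correction, where even 94 reaches only the 80% it was designed for.

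A second reply is that items 1 and 2 are conservative. The correlation of 0.7 is described that way, and the Data Analysis Plan expects ANCOVA, which is more powerful than a t-test. On item 2's inputs:

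- An assumed baseline correlation of 0.3 to 0.5 gives 74% to 82% power at 74 and 84% to 90% at 94. Reaching .85 at 74 needs about 0.56.
- An assumed intraclass correlation of 0.5 gives 82% at 74 and 90% at 94. Reaching .85 needs about 0.45 at 74 or 0.60 at 94.

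These show that 70% is an unadjusted figure that could be pessimistic. They do not support the .85, because the protocol states no baseline correlation and no intraclass correlation other than 0.7.

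A third reply is that the .85 may come from the initial power estimation or the cited study rather than from items 1 and 2. It may, and so this is not proof of a slip in a known calculation. But no inputs are given, and the figure conflicts with the calculations that are shown.

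The practical consequence is also limited. At the stated target of 100, power is at least 83% on either set of inputs, and at 94 at least 80%. The shortfall below 80% arises if enrolment stops near 74 and the SD is close to 4.0.

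**Conclusion.** The concern holds. The .85 in Section 7 follows from no inputs stated in the protocol. The first calculation exceeds it (91% at 74, 96% at 94) and the corrected one falls short (70% and 80%). The chance of missing a true 2-point benefit at 74 is therefore about 9% with SD 3.0 and about 30% with SD 4.0. The protocol does not settle which SD applies, and shorter stay does not explain the rise from 54 to 94.

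These figures assume a two-sided unadjusted comparison of patient means, an intraclass correlation of 0.7, the stated number of sessions for every patient, and no dropout.

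A related inconsistency is the target number. The Abstract gives 94–104, the tracking and randomization text in Section 4 gives 74–94, and Section 7 gives 100. The value of 100 lies within the Abstract's range, and Section 7 explains the increase. The real conflict is with the 74–94 still stated as the accrual goal and completion number.

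**What to change.** - In Section 7, replace the .85 with power at 74, 94 and 100 tied to stated inputs. Unadjusted, this is 70%, 80% and 83% on item 2's inputs, and 91%, 96% and 97% on item 1's.
- State which SD the trial relies on and why. Say that the move from 3.0 to 4.0, not the shorter stay, produces the larger sample size.
- If credit is taken for ANCOVA, a lower intraclass correlation or the cited study, give the value used and restate power from it.
- Delete the assurance about 74, or make it conditional on SD 3.0.
- Use one target number in the Abstract, the tracking and randomization text of Section 4, and Section 7.
- In the randomization text, remove the per-group label from the 25% and 50% balance checks. A quarter of 74–94 is 18.5–23.5 and half is 37–47, so the figures shown are totals.

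The cost is protocol wording only. The design and analysis are unchanged, no patients are added, and the existing target only needs stating consistently. The stated power becomes less favourable unless SD 3.0 can be justified.

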We propose to enroll 94-104 acute adult burn patients hospitalized in the Johns Hopkins Bayview Medical Center's Johns Hopkins Burn Center (Burn Intensive Care Unit) who have sustained burns  $\geq 2\%$  and  $\leq 40\%$  total body surface area (TBSA  $\geq 2\%$  &  $\leq 40\%$ ). Subjects will be randomized to either a fentanyl + saline ("usual care" - UC) condition, or to fentanyl plus ketamine (K + UC) condition. Subjects in the K + UC condition will receive low-dose, slow-infusion ketamine using methodology previously employed in the small clinical trials reviewed in background section (see information below on medications, dosing, timing etc.). Subjects in the UC condition will receive fentanyl plus normal saline whereas those in the study drug arm will receive fentanyl plus ketamine. It is hypothesized that subjects in the K + UC condition will have superior pain relief with reductions in primary and secondary hyperalgesia, as well as reductions in allodynia. It is also hypothesized that adjunctive ketamine will be associated with an opiate sparing effect, reductions in symptoms of acute stress disorder, posttraumatic stress disorder, major depressive disorder and sleep disturbance during the study and for up to one month follow-up in the acute post-burn period.

b. DOSING -

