# Tracking eligible-consenting and eligible-not-consenting patients:

Subjects who sign a consent form, but do not initiate protocol treatment for any reason (i.e., subjects who are screen failures), will have study data removed from the database and will not count towards completing our accrual goal of 74-94 subjects. The study coordinator will generate a list - that does not contain PHI - of all burn and age eligible admissions in order to maintain a minimal dataset of variables necessary to characterize the group of study eligible participants who consent with those who do not consent. These data will be used to test the representativeness of the obtained sample with the population of eligible burn admissions who do not consent. These data will enable quantitative statement of generalizability of study findings and to ascertain whether any pertinent subject study characteristic contributed.

Randomization: Group assignment of consecutively admitted and eligible patients providing informed consent will be made according to an a priori, randomly generated, list of 4-digit numbers (numbers will account for non-completers, lost to follow-up, side effects, etc). Participants will be allocated to condition on a random basis in randomly stratified blocks of 2, 4, and 6 to ensure that near-equal group numbers are assigned to each condition at key point throughout the study timeline. Those participants assigned an odd number will be allocated to Group 1 (e.g., Usual Care Plus Saline), and participants assigned an even number will be allocated to Group 2 (e.g., Usual Care Plus Ketamine).

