Pharmacy's role in policy decision-making with JHBMC Pharmacy and Therapeutics as well as in preparing the drug and delivery system.

i. JHB Pharmacy and Therapeutics Policy - discussed ketamine for research purposes in clinical setting, arrived at definitive decision in consultation with research pharmacist [name] at JHBMC and the results of her discussion with [name], Director of Interventional Research Pharmacology at JHBMC.

ii. The Ketamine Project team is adding [name] as Co-Investigator on the project for the role and tasks delineated here.

[name] has completed the "Drug Build" for the project. Specifics will be provided. She and [name] (see next) collaborate on the "Order Build" and "Drug Build" to ensure the accurate and timely delivery of study drug to study participants. The study drugs (Ketamine as well fentanyl and saline) will be delivered in plain, nondescript identical delivery system for both study drug and usual care preparations. This allows blinding of provider/prescriber, nurse and patient.

iii. The IRB-approved protocol was presented by [name] at the January 2017

JHMBC Pharmacy & Therapeutics Committee (P&T) meeting for approved use in hospitalized patients. The process for approval of clinical policy versus IRB-approved protocols are through the same committee. Full approval was given at the next P&T Committee meeting by all necessary governing bodies for the use of ketamine in this IRBapproved protocol. The pharmacy and [name] in particular, will continue to work with the Ketamine study team to coordinate provision of study materials in a blinded fashion as described next.

iv. Once the Ketamine Project Management Team identifies and consents a participant, the pharmacist will then randomize the subject based on the schema provided by the ICTR database and statistician as described above. Based on group assignment, the pharmacy will prepare the appropriate medication / placebo / study drug, deliver this to the BICU in identical bags labeled in a blinded fashion. Despite being blinded, the label will include all elements required by law.

[name] Clinical Research Pharmacist Johns Hopkins Bayview Medical Center [name]

[name] has begun the "Order Build" for the order set to be entered in the BICU EPIC. [name], Application Coordinator III Johns Hopkins Health Systems [contact]; IT@jh EPIC

5. Training House Staff and Nursing on Ketamine Protocol

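### The enrolment targets of 94–104, 74–94 and 100 are not interchangeable: on the plan's corrected assumptions power is about 70% at 74, 80% at 94 and 83% at 100, so the statements that 74–94 gives .85 and that 74 suffices do not hold

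*Combined protocol and SAP*

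**What the plan says.** Three targets stand in the current text.

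- *1. Abstract*: "We propose to enroll 94-104 acute adult burn patients".
- *4. Study Procedures*, paragraph on tracking consenting and non-consenting patients: people who consent but never start protocol treatment "will not count towards completing our accrual goal of 74-94 subjects". The randomization text that follows also gives 74–94 as study completion.
- *7. Study Statistics*: 74–94 participants (37–47 per condition) are said to give a power of .85. Then "the total target sample size will be increased to n= 100". Then, because funding is for one year, "Should funding end before 94 participants are enrolled the study will have more than sufficient power to address the primary objectives (n=74").

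The two calculations behind these numbers are in the sample size part of Section 4. The first (7-day stay, 14 sessions, SD 3.0) asks for 27 per arm, 54 in total. The second, labelled as corrected (5.5-day stay, 11 sessions, SD 4.0), asks for 47 per arm, 94 in total. Both use 80% power, not 85%.

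On interim work, Section 7c reads "Statistical plan including sample size justification and interim data analysis. Described above". Section 7 also gives the institute that helped build the randomization model a part in "preparing interim reports, and in designing and conducting both preliminary and final statistical analyses".

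**The concern.** A trial needs one planned size, because the power statement and the moment of final analysis both depend on it. Here 74, 94, 100 and 104 can each be read as the planned end. The smallest comes with an assurance that power is more than adequate. If recruitment is slow and the trial closes at 74, the investigators could cite that sentence, although the plan's own corrected calculation asks for 94. The risk is a trial that closes below its 80% goal while its protocol says otherwise, so that a null result on pain is read as more informative than it is.

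**Working it through.** **Inputs** (sample size part of Section 4): difference 2.0 NAS points; within-patient correlation 0.7; 1:1 allocation; 5% level. Case A has SD 3.0 and m = 14 sessions. Case B, the corrected case, has SD 4.0 and m = 11. Sidedness is not stated; two-sided reproduces the plan's figures.

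**Step 1. Reproduce the plan.** Design effect DE = 1 + (m − 1) × 0.7. Patients per arm = (independent observations per arm from a two-sample t-test) × DE / m.

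- Case A: DE = 1 + 13 × 0.7 = 10.1; 37 × 10.1 / 14 = 26.7, so 27 per arm. Matches 54 in total.
- Case B: DE = 1 + 10 × 0.7 = 8.0; 64 × 8.0 / 11 = 46.5, so 47 per arm. Matches 94 in total.

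**Step 2. Power at each stated size.** The SD of a patient's mean is s = SD × √(DE / m).

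- Case B: s = 4.0 × √(8.0/11) = 3.41.
- Case A: s = 3.0 × √(10.1/14) = 2.55.

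The normal approximation is power = Φ(2.0 / (s × √(2/n)) − 1.96), with n per arm. For Case B at n = 37: 3.41 × √(2/37) = 0.793; 2.0/0.793 = 2.52; Φ(0.56) = 0.71. The t-test gives 0.70. In the same way:

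| Total N | Case B, SD 4.0 (t / normal) | Case A, SD 3.0 (t / normal) |
|---|---|---|
| 74 | 70% / 71% | 91% / 92% |
| 94 | 80% / 81% | 96% / 97% |
| 100 | 83% / 83% | 97% / 98% |
| 104 | 84% / 85% | 98% / 98% |

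**Step 3. Compare with Section 7.** The .85 given for 74–94 reproduces at neither end of the range in either case. In Case B it needs 53 per arm, 106 in total, just above the Abstract's upper limit. In Case A every listed size exceeds it.

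**Step 4. Where 74 comes from.** Neither calculation produces 74. The first cites it as the number of eligible patients expected, against a requirement of 54.

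**Step 5. A knock-on inconsistency.** The randomization text schedules baseline balance checks at 25% (about 19–24 per group) and 50% (about 37–47 per group) of completion, with completion at 74–94. But 74/4 = 18.5, 94/4 = 23.5, 74/2 = 37 and 94/2 = 47, so those are total counts labelled as per group. As written, the halfway check falls at the end of the trial.

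**The case against.** **The targets can be read as a sequence.** Section 7 reports 74–94 as advice received and then settles on 100; the Abstract's range contains 100; the 74–94 in Section 4 may be unrevised text. That is fair as to intent. But it leaves 74 accepted as a fallback and .85 unsupported on the corrected inputs, both in the section that settles on 100.

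**74 is adequate in one of the plan's own cases.** True: with SD 3.0 its power is 91–92%. But the plan labels the SD 4.0 case as the correction. The SD, not the shorter stay, drives the gap: DE/m is 10.1/14 = 0.72 in one case and 8.0/11 = 0.73 in the other. The text explains the shorter stay but not the larger SD.

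**A one-sided test would rescue 74.** At a one-sided 5% level, Case B needs about 36.5, so 37 per arm, for 80% power. The plan's 47 per arm would then not reproduce, and .85 would still need 43 per arm.

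**A stronger reading is tempting: that the 5% error rate is lost.** A reader might infer this from the range of stopping sizes, the undefined interim work, and the pharmacist's instruction to "randomize the subject based on the schema provided by the ICTR database and statistician", which comes from the institute that will also help with the analysis. The documents do not support it. The only stated reason for stopping short is the end of funding, which does not depend on results; one analysis at a size fixed that way keeps 5%. No outcome test is planned at 74 or 94. The Data Analysis Plan uses the term preliminary analyses for checks of distributional assumptions, and the only timed looks are baseline balance checks. Supplying a randomization schema does not show that the analyst holds the allocation list. The documents do not exclude outcome looks by arm or an unblinded analyst, but they show neither.

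**Conclusion.** The targets conflict, and the choice between them matters. On the plan's corrected assumptions power is about 70% at 74, 80% at 94 and 83% at 100. The .85 for 74–94 and the assurance about 74 are wrong in that case and hold, as minimum values, only with SD 3.0 and 14 sessions. This rests on a two-sided 5% test, the plan's own difference, SD and correlation, and no loss of patients.

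The type I error point is a conditional illustration only. If the arms were tested unadjusted and accrual stopped at the first p < 0.05, the error rate would be 7.2% with looks at 74 and 94, and 8.0% with a further look at 100. The plan contains no such procedure.

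**What to change.** 1. State one target, 100, in the Abstract, in the tracking and randomization text of Section 4, and in Section 7. Define it consistently with the existing rule that those who consent but never start protocol treatment do not count.
2. State that accrual ends at 100 or on the funding end date, whichever comes first, and that this is decided without sight of outcomes by arm.
3. Replace the .85 statement and the assurance about 74 with the power on the corrected assumptions: about 83% at 100 and about 70% at 74.
4. Restate the 25% and 50% balance checks as 25 and 50 participants in total.
5. Where Section 7c points to interim analysis, say that the arms will not be compared on pain or medication requests before the final analysis. Keep the baseline balance checks and the independent medical monitor's safety review.

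The cost is protocol and SAP wording. It asks for no patients beyond the 100 that Section 7 already chooses.
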